1.3 Secondary Objectives

1.3.1 Cohort 1

- To evaluate effects of abemaciclib on phospho-RB (S807/811), tumor cell proliferation (Ki67) and tumor cell death (CC3, p21) by immunohistochemistry (IHC).
- To investigate pharmacokinetics of abemaciclib in participants with recurrent GBM.
- To investigate the safety profile of abemaciclib in participants with recurrent GBM.

1.3.2 Cohort 2

- To investigate the radiographic response (RR) to abemaciclib.
- To investigate median progression free survival (PFS) and overall survival (OS) of participants with recurrent GBM receiving treatment with abemaciclib.
- To investigate pharmacokinetics of abemaciclib in participants with recurrent GBM.
- To investigate the safety profile of abemaciclib in participants with recurrent GRM

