Once confirmed and allocated to the proper tubes, all tissue samples EXCEPT for the tubes labeled 5 (CE-IM) and 6 (CE-RNA) should be snap frozen and stored at the local site at -70 degrees Celsius or lower temperature until the local pathologist has finalized the clinical diagnosis and confirmed that tissue is no longer required for diagnosis. Tissue for the immunologic studies labeled 5 (CE-IM) should be fresh preserved tissue. Tissue labeled 6 (CE-RNA) should be frozen on dry ice without OCT or LN2.

If more tissue is available, an additional 200mg or larger sample should be sent fresh to the appropriate hospital research lab for establishment of a participant primary cell line (serum free, neurosphere methods) by the site's standard procedures. All remaining tissue from the resection should then be processed in a routine manner (formalin fixation and paraffin embedding) for clinical pathologic interpretation.

Both types of tissue (fresh tissue and FFPE) will be processed for correlative studies. Samples for tissue PK analysis should be sent to the Pharmacoanalytical Shared Resource, under the direction of [name] at The Ohio State University (OSU). Samples for tissue PD analysis and tissue microenvironment should be sent to [name] at DFCI. Samples for immunologic assays should be sent to [name] at UCLA.

Pharmacokinetic (PK) Samples:

Once local collection and analysis are complete, tissue samples for PK analysis [tubes labeled 1 (CE-PK), 3 (NCE-PK)] should be shipped to the address below approximately 30 days after surgery.

Preparing the shipment

E-mail the DFCI Coordinating Center at [contact] at least 24 hours prior to shipment of samples to confirm the receiving lab is aware of the shipment.

Samples should be stored in cardboard boxes (5 1/8" x 5 1/8" x 2", LxWxH).

- Organize the samples by patient and timepoint in the box.
- Do not store in plastic bags (they break on dry-ice and labels will detach).
- A copy of each of the PK sample collection forms for the respective patients or a sample list should be included with each shipment. To prevent problems with illegible writing on tubes, consider numbering them (in addition to sample label) and numbering samples on the sample sheet.
- Note the study number, PI, and the drugs used/to be measured.
- A name, phone number, and email address should be included with samples so that receipt can be acknowledged.

Shipping

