- All samples should be shipped via overnight express courier in insulated containers with enough dry ice to maintain the samples in a frozen state.
- Tissue PK samples should be sent on Monday through Wednesday (never on Thursday. Friday, weekends, or days prior to a holiday) to:

The OSUCCC Pharmacoanalytical Shared Resource Attn: [name] [name]

[contact] [contact] Email: [contact]

Upon shipment, send a notification with tracking number to the DFCI Coordinating Center at [contact] and OSUCCC Pharmacoanalytical Shared Resource at [contact]

Pharmacodynamic (PD), Tumor Microenvironment Samples, and Single-Cell RNA Sequencing Samples:

Once local collection and analysis are complete, tissue samples for PD analysis [tubes labeled 2 (CE-PD), 4 (NCE-PD)] and single-cell RNA sequencing [tube labeled 6 (CE-RNA)] as well as 10 slides from study surgery, and 20 slides from archived samples for PD and tumor multiplexed IF microenvironment analysis should be shipped to the central site (DFCI, [name], [name], [name]) within 30 days after surgery.

- Email the DFCI Coordinating Center at [contact] at least 24 hours prior to shipment of samples to confirm the receiving lab is aware of the shipment.
- A memorandum indicating the study, the date of submission, name of study site submitting the tissue, and a list of contents. The DFCI Coordinating Center will supply a template memorandum to sites at the time of the SIV or upon request.
- Include copy of the pathology and surgical reports for the sample being submitted

Samples should be sent on a Monday through Thursday (never on Friday, weekends, or days prior to a holiday) to:

[name] (attn.: Adult Path CRC)
Dana-Farber Cancer Institute
Center for Molecular Oncologic Pathology - JF215B
[name]
Ph [contact]

Upon shipment, send a notification with tracking number to the DFCI Coordinating Center at NeuroOnc [contact]

Immunologic Samples:

Samples for immunologic assays [fresh-preserved tumor tissue in tube labeled 5 (CE-IM), FFPE slides from the protocol surgery, archival FFPE slides from prior surgery, and whole blood] should be shipped via FedEX for overnight delivery directly to UCLA. Guidelines for submission of these immunologic samples as follows (please see Table 9.2 below for details):

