Plasma PKs will be batch shipped when requested by the DFCI Coordinating Center.

Preparing the shipment

E-mail the DFCI Coordinating Center at [contact] at least 24 hours prior to shipment of samples to confirm the receiving lab is aware of the shipment.

Samples should be stored in cardboard boxes (5 1/8" x 5 1/8" x 2", LxWxH).

- Organize the samples by patient and timepoint in the box.
- Do not store in plastic bags (they break on dry-ice and labels will detach).
- A copy of each of the PK sample collection forms for the respective patients or a sample list should be included with each shipment. To prevent problems with illegible writing on tubes, consider numbering them (in addition to sample label) and numbering samples on the sample sheet.
- Note the study number, PI, and the drugs used/to be measured.
- A name, phone number, and email address should be included with samples so that receipt can be acknowledged.

Shipping

- All samples should be shipped via overnight express courier in insulated containers with enough dry ice to maintain the samples in a frozen state.
- Tissue PK samples should be sent on Monday through Wednesday (never on Thursday. Friday, weekends, or days prior to a holiday) to:

The OSUCCC Pharmacoanalytical Shared Resource Attn: [name] [name] [contact]

[contact]

Email: [contact]

Upon shipment, send a notification with tracking number to the DFCI Coordinating Center at [contact] and the OSUCCC Pharmacoanalytical Shared Resource at [contact]

Archival Tissue Samples for Screening and Correlative Studies

Guidelines for submission of archival tumor tissue and for PD and tumor antigen presentation and microenvironment correlative studies at DFCI:

- A memorandum indicating the study, the date of submission, name of study site submitting the tissue, and a list of contents. The DFCI Coordinating Center will supply a template memorandum to sites at the time of the SIV or upon request.
- Include copy of the pathology, surgical, and genomic profiling/sequencing reports for the sample being submitted

• Email the DFCI Coordinating Center at [contact] at least 24 hours prior to shipment of samples to confirm the receiving lab is aware of the shipment.

Samples should be sent on a Monday through Thursday (never on Friday, weekends, or days prior to a holiday) to:

[name] (attn.: Adult Path CRC)
Dana-Farber Cancer Institute

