13. STATISTICAL CONSIDERATIONS

13.1 Study Design

This will be an open label Phase II trial in participants with recurrent GBM. Cohort 1 and Cohort 2 will enroll concurrently. In Cohort 1, to ensure that adequate abemaciclib penetrates into the tumors and inhibits cellular proliferation, 15 participants with recurrent GBM who require reoperation will be treated with abemaciclib prior to surgery. After recovery from surgery, participants will receive abemaciclib until disease progression or the development of unacceptable toxicities. In Cohort 2, participants will receive abemaciclib without undergoing prior surgery. The two cohorts will be analyzed separately.

In Cohort 1 we will attempt to characterize the pharmacokinetic (PK) uptake of abemaciclib in brain. A single-time point brain-to-plasma ratio will be calculated for each participant with a paired plasma and brain sample, followed by a descriptive statistical analysis (mean, SD, CV% or median (range)). In addition, both a naive pool strategy of all brain samples as well as a non-linear mixed effect approach will be explored in an attempt to provide a better estimate of time-course of brain uptake, the total brain exposure over a dosing interval (AUC0-24) and the brain-plasma tissue partitioning coefficient (Kpt).

Cohort 1 will also assess for pharmacodynamic (PD) evidence of target inhibition in brain tissue. We will evaluate tumor tissue after treatment with abemaciclib for reduced RB1 signaling,

cellular proliferation, and increased cell death by immunohistochemistry for pRB1, Ki67, and cleaved caspase 3. The IHC effects will be evaluated by pathologist manual scoring of each marker as well as morphometric techniques to determine change relative to pre-abemaciclib biopsy which will also be stained. These results will be compared to a group of 15 patient samples who received treatment only with standard of care TMZ and RT. Results of the two cohorts will be compared statistically to determine whether significant changes are noted.

The primary goal of Cohort 2 is to determine the therapeutic efficacy of abemaciclib as measured by PFS6. Treatment duration will be measured in 4-week cycles. Participants will remain on treatment until tumor progression, as long as there are no unacceptable toxicities. Responses will be assessed by clinical examinations every 4 weeks and MRI scans every 8 weeks.

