13.2 Endpoints

- 13.2.1 Cohort 1
- 13.2.1.1 Primary endpoint
 - o Abemaciclib levels in tumor tissue
 - Pharmacokinetics
- 13.2.1.2 Secondary endpoints
 - o Effects on tumor cell proliferation and tumor cell death
 - Safety
- 13.2.1.3 Exploratory endpoints
 - o Effects of abemaciclib on primary GBM cell lines
- 13.2.2 Cohort 2
- 13.2.2.1 Primary endpoint
 - o PFS6
- 13.2.2.2 Secondary endpoints
 - o Radiographic response rate
 - Median progression free survival
 - o Overall survival
 - Pharmacokinetics
 - o Safety
- 13.2.3 Exploratory endpoints
 - Correlate benefit from abemaciclib treatment with molecular phenotype/genotype of tumor
 - o Investigate mechanisms of resistance to abemaciclib by examining tumor tissue obtained from patients who progress on treatment, when available, with pretreatment tumor.

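### The plan does not mask the Cohort 1 IHC scorer to pre/post or treatment status, although participants' slides reach the laboratory with surgical and pathology reports

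*Combined protocol and SAP*

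**What the plan says.** Section 13.2 lists "Effects on tumor cell proliferation and tumor cell death" among the secondary endpoints of Cohort 1, and section 1.3 makes the IHC markers a secondary objective. On measurement, section 13.1 says: "The IHC effects will be evaluated by pathologist manual scoring of each marker as well as morphometric techniques". The purpose is "to determine change relative to pre-abemaciclib biopsy which will also be stained". The same section then compares the results with 15 samples from patients treated only with temozolomide and radiotherapy. Section 13.4 adds quantitative IHC and says that pharmacodynamic results will in general be summarised descriptively.

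On specimen flow, section 9.2 says "Samples for tissue PD analysis and tissue microenvironment should be sent to" a named recipient at DFCI. The shipment contains "10 slides from study surgery, and 20 slides from archived samples for PD" and microenvironment work, is due within 30 days after surgery, and carries a memorandum listing its contents. The instruction continues: "Include copy of the pathology and surgical reports for the sample being submitted". The separate archival instructions in section 9.2 say: "Include copy of the pathology, surgical, and genomic profiling/sequencing reports for the sample being submitted".

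Appendix B, section 3.6.1, asks that participant reports be de-identified where feasible. None of these sections, nor section 9.2.3 on IHC, mentions masking of the scorer, coded slides or reading order.

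**The concern.** A manual IHC score involves judgement. Section 13.1 states the direction that the investigators hope to see: less RB1 signalling, less proliferation, more cell death. A scorer who can tell exposed from unexposed tissue may lean that way without intending to, and such a lean goes straight into the before/after contrast.

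The readout matters more since the amendment described in section 2.4. Cohort 2 showed limited benefit, and the surgical cohort continues in order to learn about drug levels and drug effect in tumour and to help explain the limited activity. A fall in pRb or Ki-67 produced by the reader would suggest that the target was inhibited, and would point to the wrong explanation.

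A smaller gap adds to this. Two scoring methods are planned, and the plan does not say which one is the result if they disagree.

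**Working it through.** The plan gives no alpha, power, effect size or SD for the IHC endpoint, so there is no figure of its own to reproduce. The check is mainly a comparison of sections.

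**What the sections establish together**

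1. Method: manual plus morphometric scoring, as change from pre-treatment tissue (13.1).
2. Routing: archived and study-surgery slides both go to one DFCI laboratory (9.2).
3. Information travelling with them: a contents list and the pathology and surgical reports, plus genomic reports under the archival instructions (9.2). The slide counts also differ, 10 against 20.
4. Safeguards: de-identification only (Appendix B, 3.6.1). This hides who the patient is, not whether the tissue was taken before or after drug.
5. Not stated: whether the person who scores sees the reports, how comparator slides are labelled, whether reports accompany the comparators, and how slides are grouped into staining runs.

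So the information that would unmask a reader reaches the laboratory, and the plan has no step that stops it there.

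**Illustration of size**

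These are assumptions, not features of the plan: a two-sided 5% t-test, no true drug effect, and a systematic reading shift of b, in SDs of the paired difference. For the comparator rows, the shift affects treated pairs only and the SD is equal in both groups. The sample sizes come from the documents: 15 participants (13.3), and comparators of 15 (13.1) or 10 (2.5).

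- Paired: noncentrality = b × √15 = 3.873b, df = 14.
- Two groups: noncentrality = b / √(1/n1 + 1/n2). For 15 v 15 this is 2.739b, df = 28. For 15 v 10 it is 2.449b, df = 23.
- False-positive rate = P(|T| > t at 0.975), with T noncentral t.

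| Contrast | b = 0.10 | b = 0.25 | b = 0.50 |
|---|---|---|---|
| 15 pairs: noncentrality | 0.387 | 0.968 | 1.936 |
| 15 pairs: false-positive rate | 0.065 | 0.147 | 0.438 |
| 15 v 15: noncentrality | 0.274 | 0.685 | 1.369 |
| 15 v 15: false-positive rate | 0.058 | 0.101 | 0.262 |
| 15 v 10: noncentrality | 0.245 | 0.612 | 1.225 |
| 15 v 10: false-positive rate | 0.056 | 0.090 | 0.217 |

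A small shift is nearly harmless and a moderate one is not. The documents do not show where this trial would fall.

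**The case against.** The best defence has four parts.

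- **Limited role.** The Cohort 1 primary endpoint is drug concentration by LC-MS/MS, which no IHC reader can influence. No decision rule depends on IHC. This stands, and it limits the weight of the point.
- **Descriptive analysis.** Section 13.4 leans that way. But section 13.1 also calls for a statistical comparison to look for significant changes, and a biased reading moves a descriptive mean change by the same amount as a tested one.
- **Morphometry and a comparator.** Both can reduce the problem. Morphometry protects the conclusion only if its place relative to the manual score is fixed in advance. The comparator protects only if it is read under the same conditions. It is also described differently in sections 13.1 (15 samples), 2.5 (10 patients) and 9.2 (untreated patients from another study).
- **Reports have other uses.** DFCI also performs central pathology review (14.1) and confirms tissue viability (9.2), so the reports may never reach the scorer. That is possible, and the documents do not settle it.

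A reader might also infer more than the text supports:

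- **That the scorer knows the status of each slide.** The plan is silent on masking; it does not describe unmasked reading.
- **That the two slide sets arrive months apart and are stained in different runs.** The pharmacodynamic instruction in section 9.2 puts both sets in a shipment within 30 days after surgery. Other deadlines (60 days from registration for archived tissue, 60 days from surgery for study tissue) make separate arrival possible but not planned. Receipt is not staining, and run differences that vary between participants would mostly add noise.
- **That the comparison is uncontrolled.** Section 13.1 names an external group.
- **That the false-positive rate is 15-44%.** Those values need an assumed shift of 0.25 to 0.50 SD and a paired t-test that the plan does not name.

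**Conclusion.** The point holds as a gap in the procedure. The IHC endpoint relies in part on manual scores, the participants' slides travel with reports that reveal pre/post status, and nothing in the plan masks the scorer. The manual scores are therefore open to bias toward lower pRb and Ki-67. Whether bias will occur, and how large it would be, cannot be derived from the documents. The ranges of about 6-44% (15 pairs) and 6-26% (15 v 15) only show sensitivity, under the assumed shifts and tests set out above.

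This is a worthwhile, low-cost improvement to a secondary endpoint. It does not touch the Cohort 1 primary endpoint or anything in Cohort 2. Which of the two scores should be the reported one is a matter of preference; the point requires only that the choice be made before scoring.

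**What to change.** Add to sections 13.1 and 9.2.3:

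- Existing Coordinating Center staff code the archived, protocol-surgery and comparator slides so that labels and slide counts do not reveal origin.
- The pathology, surgical and genomic reports stay with the Coordinating Center or the central reviewer and are withheld from the IHC scorer until scores are locked.
- Slides are read in random order, with comparators mixed in.
- Each participant's pair is stained in the same run where feasible.
- The plan states, before any scoring, whether the manual or the morphometric score is the reported result, and how the other will be used.

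No extra patients or tissue are needed. The cost is relabelling work and a slightly later readout, because slides wait until a pair or batch is complete. Section 9.2 already has sites cut the FFPE slides for UCLA only on central request after recruitment ends, so central timing of slides is familiar here. The change has to be in place before scoring, since masking cannot be restored afterwards.

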13.2 Endpoints

- 13.2.1 Cohort 1
- 13.2.1.1 Primary endpoint
 - o Abemaciclib levels in tumor tissue
 - Pharmacokinetics
- 13.2.1.2 Secondary endpoints
 - o Effects on tumor cell proliferation and tumor cell death
 - Safety
- 13.2.1.3 Exploratory endpoints
 - o Effects of abemaciclib on primary GBM cell lines
- 13.2.2 Cohort 2
- 13.2.2.1 Primary endpoint
 - o PFS6
- 13.2.2.2 Secondary endpoints
 - o Radiographic response rate
 - Median progression free survival
 - o Overall survival
 - Pharmacokinetics
 - o Safety
- 13.2.3 Exploratory endpoints
 - Correlate benefit from abemaciclib treatment with molecular phenotype/genotype of tumor
 - o Investigate mechanisms of resistance to abemaciclib by examining tumor tissue obtained from patients who progress on treatment, when available, with pretreatment tumor.

13.3 Sample Size/Accrual Rate

A sample size of 15 participants is planned for the surgical sub-study (Cohort 1), with an accrual rate of 2-3 participants per month. This results in an anticipated enrollment period of 5-8 months

for Cohort 1.

Thirty-two participants will be accrued to Cohort 2 and will occur concurrently with Cohort 1. With an accrual rate of 4-5 participants per month, the anticipated enrollment period will be 7-9 months for Cohort 2.

The primary endpoint for Cohort 2 will be the proportion of participants who are progression free at 6 months (PFS6). Historical comparison data suggest that ineffective therapies in recurrent GBM have a PFS6 rate of approximately 9-16% (Lamborn et al., 2008; Wong et al., 1999). The sample size was chosen to discriminate between 15% and 35% PFS6 rates for the GBM patients. With accrual of 32 GBM patients, the trial would be considered successful if 8 achieved PFS6. This yields 0.92 power to detect a 35% PFS6 rate, with a 0.90 probability of rejecting the treatment regimen if the PFS6 rate is only 15%.

Since the primary endpoint is PFS6, analyses will be not performed until the 6 month PFS status of all participants is determined (or the participant has been permanently censored for PFS for reasons such as loss-to-follow-up or initiation of alternative therapies).

For the primary endpoint of PFS6, participants without documentation that they are progression free at 6 months – no progression at the 24 week scan – will be considered failures. Additional information about PFS will be provided using Kaplan Meier curves. For those analyses participants will be censored for PFS at the date of the last scheduled scan if they initiate alternative therapy or cease to have regularly scheduled follow up scans.

13.4 Analysis of Secondary and Exploratory Endpoints

Response rate will be the proportion of participants with measurable disease who experience complete or partial radiographic response determined by the RANO Criteria (Wen et al., 2010). Progression free survival, PFS6, and overall survival will be calculated using standard statistical methods. Safety will be summarized using descriptive statistics. Participants in Cohort 2 will not be replaced for any reason. If a subject enrolled in Cohort 1 is found at the time of on-treatment re-resection to have only necrosis and not recurrent disease, then s/he may remain on treatment but should be replaced for evaluation of endpoints.

In Cohort 1 & 2 plasma, and Cohort 1 tumor tissue levels of abemaciclib will be determined by liquid chromatography coupled with tandem mass spectrometry. Descriptive details of steady-state trough plasma levels, CSF and tumor tissue concentrations and tumor tissue to plasma ratios will be provided.

Other pharmacodynamic studies including immunohistochemistry and quantitative IHC analysis will be performed as in Section 9.0. Effects of abemaciclib on tumor cell proliferation and tumor cell death will be measured using immunohistochemistry for pRB1, Ki-67 and Cleaved Caspase 3. In general the pharmacodynamic and neuro-imaging results will be summarized in a descriptive manner with comparison between pre- and post-treatment assay results when possible.

Beyond the assessment of "success", more detailed analyses of the biological correlate data are exploratory. The statistical analysis will depend on the amount and quality of the data obtained as well as the overall success of the treatment.

